3.1.4 Allocation to Interventional Group

Study randomization will be performed in a 1:1 fashion using the Urn Randomization program (<https://health.uconn.edu/community-medicine/programs/health-services-research-unit/project-match/urn-randomization/>) while balancing sex and AF type (paroxysmal and non-paroxysmal). The master list of study assignments will be kept by the study coordinator in a password protected and encrypted computer.

3.2 Study Endpoints

3.2.1 Primary Study Endpoints

The primary endpoint of the study is the recurrence of atrial arrhythmia post-ablation. The primary endpoint is defined as a non-self-terminating bout of atrial fibrillation, atrial flutter, or atrial tachycardia >30 seconds in duration following the 90-day post-ablation blanking period.

3.2.2 Secondary Study Endpoints

AF burden will be compared among study groups as a secondary outcome variable. AF burden will be measured from the 30 day monitors.

3.2.3 Primary Safety Endpoints [if applicable]

The primary safety composite outcome is defined by occurrence of one or more of the following events during the 30-day period following the ablation procedure: stroke, myocardial infarction, esophageal damage, pulmonary vein stenosis, bleeding, heart failure and death.

4 Study Population and Duration of Participation

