7.6 Safety Evaluations

Comparing study adverse outcomes between the two study groups will be utilized to assess the safety of the additional ablation lesions in the investigational arm.

8 Statistical Plan

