8.4.3 Safety Analysis

All subjects entered into the study and randomized at the baseline visit will have detailed information collected on adverse events for the overall study safety analysis

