9.1 Definitions

9.1.1 Adverse Event

An **adverse event (AE)** is any symptom, sign, illness or experience that develops or worsens in severity during the course of the study. Intercurrent illnesses or injuries will be regarded as adverse events. Abnormal results of study procedures will be considered to be adverse events if the abnormality:

- results in study withdrawal
- is associated with a serious adverse event
- is associated with clinical signs or symptoms
- leads to additional treatment or to further diagnostic tests
- is considered by the investigator to be of clinical significance

Additionally, any untoward medical occurrence associated with ablation near the coronary sinus will be considered an adverse effect.

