12.1 Risks

The risks for subjects are the same as standard ablation in atrial fibrillation with the exception of slightly prolonged mapping and ablation time by approximately 5-10%. Ablation of the region near the coronary sinus is also associated with higher risk of coronary injury. However, the risk of coronary injury is low given the investigators prior extensive experience ablating in this region for peri mitral flutters and accessory pathways.

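### The primary safety composite does not name coronary artery injury, the only specific injury that section 12.1 says the added ablation makes more likely, and counts it only through a listed consequence.

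*Combined protocol and SAP*

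**What the plan says.** Section 3.2.3 makes the primary safety outcome a composite of "stroke, myocardial infarction, esophageal damage, pulmonary vein stenosis, bleeding, heart failure and death", counted over the 30 days after ablation. The Study Summary gives the same seven components and window.

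Section 12.1 describes how risk differs from a standard ablation. It names "slightly prolonged mapping and ablation time by approximately 5-10" percent, and then states that "Ablation of the region near the coronary sinus is also associated with higher risk of coronary injury". It adds that "the risk of coronary injury is low given the investigators prior extensive experience", and gives no rate.

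Three other places bear on safety:

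- Section 7.6: "Comparing study adverse outcomes between the two study groups will be utilized to assess the safety of the additional ablation lesions". It does not say which outcomes are compared or by what method.
- Section 8.4.3: all randomised subjects "will have detailed information collected on adverse events for the overall study safety analysis".
- Section 9.1.1: "any untoward medical occurrence associated with ablation near the coronary sinus will be considered an adverse effect".

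**The concern.** Section 7.6 says the arm comparison "will be utilized to assess the safety of the additional ablation lesions in the investigational arm". The one safety outcome that the plan defines, with a component list and a time window, is the composite in 3.2.3. The one specific injury that 12.1 ties to the added lesions is not on that list.

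A patient with a recognised coronary injury and no infarction, heart failure, bleeding, death or other listed event by day 30 would be recorded as having an adverse event and scored as free of the primary safety outcome. A report led by the composite could then show equal safety in the two arms while the harm anticipated in 12.1 had occurred in one of them.

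This matters more because little else in the plan would bring such a case forward. Stopping rules are marked not applicable (9.6), and safety oversight rests with the principal investigator and co-investigators (9.7, 9.7.1).

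**Working it through.** **No safety figure to reproduce.** The documents state no rate, margin, test or power for safety. The only power figure (8.3, hazard ratio 0.2 with 100 participants) concerns efficacy and does not bear on this point.

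**Step 1: how a coronary injury would be scored.**

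| Course of the injury | Composite (3.2.3) | Adverse event record (9.1.1, 9.2) |
|---|---|---|
| Leads to infarction, heart failure, bleeding, death or another listed event by day 30 | Counted | Recorded |
| Recognised, no listed event by day 30 | Not counted | Recorded |
| Never recognised, no listed event | Not counted | Not recorded |

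The second row is the gap. The third row exists because no coronary imaging is scheduled (Table 1) and laboratory evaluations are not applicable (7.4). A change of endpoint definition alone does not close it.

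**Step 2: whether the other safety provisions fill the second row.** If adverse outcomes in 7.6 means the composite, the injury is missed in the comparison too. If it means all adverse events, the injury is included, but nothing requires a separate count by arm. Neither reading supplies a definition of coronary injury. Blinded adjudication covers AF events only (3.1.3, 7.5). The clause in 9.1.1 depends on linking an event to ablation near the coronary sinus. The treating clinician knows the assignment (5.6), and the principal investigator rates relatedness (9.3).

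**Step 3: how many cases might arise.** Inputs: 100 participants randomised 1:1 (4.5, 3.1.4), so about 50 per arm; injury rate p is assumed.

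P(at least one case in 50) = 1 − (1 − p)^50

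| Assumed p | Calculation | Result |
|---|---|---|
| 0.5% | 1 − 0.995^50 | 22% |
| 1% | 1 − 0.99^50 | 39% |
| 2% | 1 − 0.98^50 | 64% |
| 5% | 1 − 0.95^50 | 92% |

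These are chances of any coronary injury, including those already counted through a listed event. If a fraction f of injuries has no listed consequence, the missed cases occur at rate p × f. The documents give neither p nor f. For illustration, p = 2% and f = 0.5 give 0.02 × 0.5 = 1%, hence 39%; p = 1% and f = 0.5 give 0.5%, hence 22%. With f = 1 the table applies unchanged; with f = 0 nothing is missed.

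**Step 4: what 50 per arm can show.** With no case among 50, the upper limit of the exact two-sided 95% interval is 1 − 0.025^(1/50) = 7.1%. This reflects the sample size and is the same with or without the fix. For the composite, if the control rate were 3% or 5% and the investigational arm were 5 percentage points higher (both assumed), Fisher's exact test at two-sided 0.05 would have about 6% power (0.062 and 0.063). Any safety comparison is therefore descriptive.

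**Step 5: whether existing data settle the matter.** Section 1.2.2 reports 4 patients in whom these connections were ablated safely. Reading that as 0 injuries in 4, the same exact upper limit is 1 − 0.025^(1/4) = 60%, so these data exclude little.

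**The case against.** The strongest reply is that the composite is not the plan's only view of safety. Section 7.6 compares adverse outcomes between the arms for exactly this purpose, 8.4.3 collects adverse events on everyone randomised, and 9.1.1 has a clause written for ablation near the coronary sinus. A recognised injury would be on record. This stands. A reader might infer that the plan cannot assess the safety of the added lesions; these sections do not support that. What they leave open is a definition, a count by arm, and a place in the primary safety result.

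It is also fair to say that the composite is not blind to coronary harm. Infarction, heart failure, bleeding and death are all routes into it. Nor is coronary injury the only difference stated in 12.1, since longer mapping and ablation time is given as well; it is the only specific injury named. A reader might further infer that the other components are background risk, equal in both arms, that dilutes a true difference. The documents give no component rates and do not show that extra lesions and a longer procedure leave those components unchanged.

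A last objection concerns the remedy. Operators who know the assignment may look harder for coronary injury in one arm, so an undefined component would invite ascertainment bias. This also stands, and the fix has to answer it.

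The protocol's rating of the risk as low does not remove the point. It rests on experience in the region for other arrhythmias and comes without a rate.

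**Conclusion.** The point holds in a limited form. The only defined safety endpoint leaves out the one specific injury that the protocol expects the added ablation to raise, and captures it only through a listed consequence within 30 days. Following the plan as written, a recognised injury without such a consequence is scored as no primary safety event.

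The size cannot be fixed from the documents, because neither the injury rate nor the share without a listed consequence is given. Under the assumed rates in the working, one or a few cases are plausible in 50 patients. At such counts, where a single case is tabulated changes what the safety result shows.

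This does not make the trial unable to assess safety, and it affects no stated power or sample-size figure. It is a gap in an endpoint definition that should be closed because closing it is cheap.

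**What to change.** In 3.2.3 and the Study Summary:

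1. Add coronary artery injury, with or without myocardial infarction, as a component. Use the existing 30-day window and state that it includes the procedure itself.
2. Give a short objective definition, based on recorded findings and applied identically in both arms, that does not depend on attributing the event to ablation near the coronary sinus.
3. State that the injury is also reported separately by arm, as a count with an exact confidence interval.

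In 7.6, say which adverse outcomes are compared.

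The cost is a few lines of protocol text and one case report form item. No imaging or laboratory test is added.

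Three limits remain. The comparison stays descriptive at 50 per arm. Silent injury is still missed. Recognition still depends partly on operators who know the assignment; the objective definition limits that influence, and the separate tabulation lets a reader see how far this component drives the composite. The composite rate may come out somewhat higher in the investigational arm, which is a difference the endpoint is there to show.

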4.1 Inclusion Criteria

- Patients with paroxysmal or persistent atrial fibrillation; AND
- Undergoing first AF ablation; AND
- Age \geq 18 years.

4.2 Exclusion Criteria

- Previous AF ablation
- Women currently pregnant;
- Mental or physical inability to take part in the study;
- Known terminally ill patients.

4.3 Subject Recruitment

Participants will be recruited from investigator clinical practices in the University of Pennsylvania Health System.

CONFIDENTIAL

This material is the property of the University of Pennsylvania.

4.4 Duration of Study Participation

Participants will be part of the study for 6 months after ablation.

4.5 Total Number of Subjects and Sites

Recruitment will end when 100 participants are enrolled at Penn.

4.6 Vulnerable Populations:

Vulnerable populations will not be targeted.

5 Study Intervention

5.1 Description

The reference therapy is pulmonary vein isolation and elimination of non-PV triggers. The investigational arm will include pulmonary vein isolation and non-PV trigger elimination, in addition to distal coronary sinus isolation.

5.2 Intervention Regimen

In the investigational group, distal coronary sinus pacing will be utilized to localize the earliest connection (aside from septal) from the coronary sinus to the left atrial musculature. Once localized focal radiofrequency lesions will be applied at the discretion of the investigator until central (septal) activation of the left atrium is noted during distal coronary sinus pacing.

5.3 Receipt

N/A.

5.4 Storage

N/A

5.5 Preparation and Packaging

N/A.

5.6 Blinding

The unblinded research coordinator will keep a master file of participant assignments. Once a participant is randomized, the investigator/clinician for the patient will be notified of the participant assignment. The remainder of the research team and the participant will be blinded to participant assignment.

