3.1.2 Study Intervention Phase

Participants will be randomized in a 1:1 fashion to 2 groups. Group 1 participants will undergo the current standard of care ablation with pulmonary vein isolation and non-pulmonary vein triggers elimination; group 2 participants will undergo coronary sinus-left atrium connection ablation, in addition to pulmonary vein isolation and non-pulmonary vein triggers. The distal coronary sinus electrode pair will be paced at an output not higher than 10mA. During pacing, the earliest activation time in the left atrium at 20 plus milliseconds after the pacing spike will be localized and targeted for ablation. Lesions will be delivered at 40 watt or less, for 30 seconds or less and titrated down using standard criteria at the discretion of the proceduralist. Stimulation for induction of AF with pacing cycle length from 250 to 180 ms or 2:1 capture

CONFIDENTIAL

will be performed from proximal coronary sinus and distal coronary sinus and at the site of left atrial to CS connection before and after ablation.

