5.7.1 Return or Destruction of Investigational Product

N/A.

6 Study Procedures

[figure not shown]
CONFIDENTIAL

This material is the property of the University of Pennsylvania.

TABLE 1: SCHEDULE OF STUDY PROCEDURES

Study Phase	Screening	Intervention: Ablation	Visit 1	Visit 2
Visit Number		0	6 weeks	6 months
Informed Consent/Assent	X			
Review Inclusion/Exclusion Criteria	X			
Demographics/Medical History	X			
Physical Examination	X		X	X
Vital Signs: BP, HR, RR	X	X	X	X
Height and Weight	X	X		
Randomization		X		
Adverse Event / Unanticipated Problems Assessment		X	X	X
12-Lead ECG	X	X	X	X
30-day Monitor		X		X

Figure 1. Study flowchart

CONFIDENTIAL

This material is the property of the University of Pennsylvania.

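### Nothing withholds the assignment from the operator until the shared PVI and trigger work is done, and the time of randomization is stated two ways

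*Combined protocol and SAP*

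**What the plan says.** **Who is told.** Section 5.6: "Once a participant is randomized, the investigator/clinician for the patient will be notified of the participant assignment". It continues: "The remainder of the research team and the participant will be blinded to participant assignment".

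**When randomization happens.** Section 8.4.3 says: "All subjects entered into the study and randomized at the baseline visit will have detailed information collected on adverse events". Table 1 has the columns "Study Phase Screening Intervention: Ablation Visit 1 Visit 2", and its only randomization mark is in the ablation column. The baseline visit list in 6.1.1 does not include randomization.

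**What the arms share.** Section 5.1: "The investigational arm will include pulmonary vein isolation and non-PV trigger elimination, in addition to distal coronary sinus isolation". Section 3.1.2 opens with "Participants will be randomized in a 1:1 fashion to 2 groups" and then describes each group's whole procedure. For the second group: "group 2 participants will undergo coronary sinus-left atrium connection ablation, in addition to pulmonary vein isolation and non-pulmonary vein triggers".

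**What is blinded.** The Study Summary and 3.1 call the trial single-blind. Sections 3.1.4 and 5.6 have a coordinator hold the assignment list. Sections 3.1.3 and 7.5 have two blinded electrophysiologists adjudicate AF events.

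**What is not stated.** No section delays disclosure until the shared steps are complete, fixes a method or completion criterion for the non-PV trigger work, or plans a comparison of the shared work between arms.

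**The concern.** The trial is meant to isolate the effect of the added CS-LA lesions, so the PVI and non-PV trigger work must be comparable in the two arms. Its extent depends on the operator's judgement. An operator who already knows the arm may search for and ablate triggers more or less persistently in one group. Any resulting difference in recurrence would enter the treatment comparison as if CS-LA ablation had caused it.

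Blinding the patient and the adjudicators protects the reporting and classification of events. It cannot correct a difference in how the shared ablation was performed.

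**Working it through.** **1. The passages side by side**

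| Section | Bearing on timing or disclosure |
|---|---|
| 5.6 | Assignment released to the patient's investigator or clinician on randomization |
| 8.4.3 | Randomization at the baseline visit |
| Table 1 | Randomization at the ablation visit; moment within the visit not given |
| 6.1.1 | Randomization absent from the baseline list |
| 3.1.2 | Randomization described first, then the whole procedure by group |

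Sections 8.4.3 and Table 1 disagree. Under the 8.4.3 timing the assignment is known before the procedure starts. Under Table 1 it may or may not be. Neither requires that the shared work be finished first.

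Section 5.6 does not use the word operator. The inference is sound, because whoever ablates must learn whether to add the CS-LA lesions. That knowledge is needed only at the point where the arms diverge.

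**2. The plan's own figure**

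Inputs from 8.3: two-sided alpha 0.05, power 0.80, 100 participants 1:1, control freedom from AF 0.7, hazard ratio (HR) 0.2, log-rank test.

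- Expected events: 50 × (1 − 0.7) + 50 × (1 − 0.7^0.2) = 15 + 3.44 = 18.44.
- Freedman's formula, events required: (1.960 + 0.842)² × (1.2/0.8)² = 17.66, or 18 after rounding up.
- Power at N = 100: Φ(√18.44 × 0.8/1.2 − 1.960) = Φ(0.903) = 0.817.

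The stated HR of 0.2 reproduces. This point does not challenge it, and the fix leaves N, alpha and power unchanged.

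**3. Illustration of the bias**

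The documents give no figure for how far unblinding might change the shared work, so the apparent HR b below is an assumption. Suppose CS-LA ablation has no effect, and unequal shared work alone produces b in favour of the investigational arm. With N = 100, control freedom 0.7, proportional hazards and no dropout:

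- Events: d = 50 × 0.3 + 50 × (1 − 0.7^b).
- Chance of a significant result favouring the investigational arm (Schoenfeld): Φ(√(d/4) × |ln b| − 1.960).

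| Assumed b | Freedom, investigational arm | Events d | False significant result |
|---|---|---|---|
| 1.0 | 0.700 | 30.0 | 2.5% |
| 0.9 | 0.725 | 28.7 | 4.7% |
| 0.8 | 0.752 | 27.4 | 8.4% |

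For b = 0.8: √(27.41/4) = 2.618; 2.618 × 0.223 = 0.584; Φ(0.584 − 1.960) = Φ(−1.376) = 0.084. Freedman's version of the same step, √27.41 × 0.2/1.8 = 0.582, also gives 8.4%, so the choice of formula does not matter here.

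The bias could equally run the other way. If less trigger work in the investigational arm raised its hazard by a factor of 1/0.8 = 1.25, a true HR of 0.2 would appear as 0.25.

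**The case against.** The best defence is that this is declared design. The trial calls itself single-blind, 5.6 says openly who is told, and an operator who must add lesions in one arm cannot stay blind throughout. Patients and adjudicators are blinded. This stands: there is no contradiction with the masking label, only a risk that could be reduced.

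Two stronger readings are tempting, and the documents do not support either.

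- *A reader might infer that the shared work is certainly done unblinded.* Table 1 gives the visit and not the moment within it, so randomization during the procedure is not ruled out. The wording in 8.4.3 is one incidental phrase in a safety paragraph, which 6.1.1 and Table 1 do not bear out. Sections 3.1.2 and 8.4.3 point towards randomization before ablation, but do not settle it.
- *A reader might infer that early randomization causes losses that 8.5 then removes, taking power below target.* The documents give no loss rate. Section 6.4 ties withdrawal to non-adherence or the participant's wish, so a patient who is not ablated is not automatically excluded by 8.5. Section 12.4 allows consent in the recovery unit before ablation, so the gap may be short. Even an assumed loss of 5 of 100 moves Freedman power only from 81.7% to 79.7%.

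A further objection concerns the remedy. Section 3.1.2 calls for AF-induction pacing ahead of and following ablation, including at the CS-LA connection site. It does not say whether this applies to both groups, or whether ablation there means the whole procedure or only the CS-LA lesions. Late disclosure could conflict with some readings. It also cannot stop an operator from returning to trigger work after disclosure. Both limits stand and are taken into the fix.

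**Conclusion.** The concern holds as an avoidable performance-bias risk together with an inconsistency in the stated time of randomization. As written, the assignment is released on randomization, and nothing delays it until the PVI and non-PV trigger work is complete.

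The size and direction of any bias are unknown. The increase from 2.5% to about 5–8% rests wholly on the assumed apparent HR of 0.8–0.9, and shows only that a modest imbalance would matter. The conclusion also rests on reading the treating investigator in 5.6 as the operator. Apart from the timing discrepancy, which needs correcting in any case, this is a cheap improvement to the design and not the repair of an error.

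**What to change.** 1. **One randomization time.** Reconcile 8.4.3 with Table 1 so that both place randomization on the ablation day.
2. **Delayed disclosure.** State in 5.6 and 3.1.4 that the coordinator gives the operator the assignment only after the shared PVI and non-PV trigger work is documented complete. The balancing factors, sex and AF type, are known beforehand, and the coordinator already holds the list.
3. **Consistency with 3.1.2.** Clarify which patients have the induction pacing and which ablation it refers to, so that any pacing done before disclosure does not require knowing the arm. The investigators must confirm that the sequence is workable.
4. **Reporting.** Record the extent of the shared work for every patient and report it by arm, marking anything done after disclosure. This does not prevent an imbalance, but it makes one visible.

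The cost is protocol wording, one communication from the coordinator during each procedure, and a few data fields. The downside is minor procedure-room logistics, and that the arm-specific step must follow the shared steps, an order the protocol does not now set.
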